### **Efficacy Endpoints Analysis**

Generalized linear mixed model (GLMM) will be used to compare the effect of treatment month on efficacy rate outcomes.

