**Study RWE-003**

Title	Real-World Evidence (RWE) of Usage of Nerivio, a Remote Electrical Neurostimulation (REN) Device In Adolescents Patients With Migraine
Sponsor	Theranica Bio-Electronics Ltd. [name]
Investigational Device	
Nerivio is a Remote Electrical Neuromodulation (REN) wearable, battery-powered medical device for the acute and/or preventive treatment of migraine with or without aura in patients 12 years of age or older. Nerivio is controlled by a mobile application. Nerivio is intended for self-administration in a home healthcare environment.
 
The device is worn on the upper arm and transmits transcutaneous remote electrical nerve stimulation by applying weak electrical pulses that invoke conditioned pain modulation (CPM) to inhibit migraine pain. Nerivio is intended for self-administration at the onset of a migraine episode.

Objectives	To evaluate the safety, utilization and efficacy of Nerivio in adolescent patients (Age 12-18) who used the Nerivio device for treating their migraine
Patient Population	Nerivio users aged 12-18 years old who registered a Nerivio account and used the Nerivio device for the acute treatment of migraine.
Sample size	The sample size will includes all Nerivio users in the age of 12-18 in the Nerivio database who treated with Nerivio at least once between Jan 01, 2021 and May 31, 2022
Inclusion criteria	

• Age between 12-18 years

• REN user across the United States who created Nerivio account on January 1st, 2021 until May 31, 2022.

• Had at least two evaluable treatments with the Nerivio device (for consistent efficacy analysis).

Exclusion criteria	

• Treatments shorter than 20 minutes will not be included in the analysis

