Study Design	
The analysis included patients at the age of 12-18 (at the day of opening a Nerivio account) with migraine across the USA who used Nerivio at least once between January 01, 2021, and May 31, 2022.
 
Treatment data will be collected through the Nerivio app (Nerivio®) which is required for treatment. Device output current is set by the user to be strong but not painful and is equivalent to treatment dosage (max device current 40 mA on 0-100 units user-facing scale). Additionally, patients can voluntarily log details about their symptoms at both treatment onset and 2-hours post-treatment status. Treatment efficacy will be measured by consistent reduction in headache pain intensity and functional disability at 2-hours post-treatment, based on data from patients who voluntarily will answer the pre and post treatment questionnaires. Safety will be assessed by the rate of device related adverse event reported by the patients.

Evaluable Treatment	
Evaluable treatment is a treatment that meets all the following criteria:
 

• Baseline and 2-hour post-treatment pain intensity and functional disability scores were recorded.

• The participant did not use any concomitant acute migraine medication during the treatment.

Efficacy endpoints	

1. Pain Relief: Reduction in pain intensity from moderate or severe (baseline score of 2 or 3) to mild or no pain (score of 1 or 0) at 2 hours post-treatment.

2. Pain Freedom: Reduction in pain intensity from mild, moderate, or severe (baseline score of 1, 2, or 3) to no pain (score of 0) at 2 hours post-treatment.

3. Functional Disability Relief: Reduction in functional disability by at least one point from baseline at 2 hours post-treatment.

4. Functional Disability Freedom: Reduction in functional disability from mild, moderate, or severe (baseline score of 1, 2, or 3) to no disability (score of 0) at 2 hours post-treatment.

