## **STATISTICAL CONSIDERATIONS FOR RWE-003 STUDY**

The study hypothesis was that treatments of migraine with the Nerivio device In adolescents will demonstrate similar results to the results previously found in adults

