### **Utilization Endpoints Analysis**

Utilization outcome will be calculated from the treatment parameters (intensity levels) and the treatment reports (usage of rescue medications), and will be presented in appropriate distribution tables.

Qualifies treatment was defined as

1 - Attacks treated with Nerivio for at least 20 minutes

2 - Pre and post treatment data were reported by the participant for the specific treatment

3 – No rescue medications were taken before and during the 2 hours post treatment, according to the participant report

Consistent efficacy will be conducted in cases where at least two qualified treatments were performed. Patients who experienced the outcome (e.g., pain freedom) in at least 50% of their reported treatments, during which they did not report the use of rescue medications, were considered responders.

Headache pain and functional disability will be rated at baseline and at 2 h post-treatment on a 4-point scale: severe, moderate, mild, or none. Migraine associated symptoms (photophobia, phonophobia, and nausea/vomiting) will be marked as present or not.

Pain relief will be calculated as a decrease from severe or moderate levels at baseline to mild or none at 2 h posttreatment.

Functional disability relief will be calculated as any improvement in disability from baseline to 2 h posttreatment.

Pain/functional disability freedom will be calculated as a decrease from any pain/disability level at baseline to none at 2 h post-treatment.

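### The month model names no baseline severity while the freedom endpoints pool mild, moderate and severe attacks, so a shift in the baseline mix could move the month effect with no change in per-attack outcome

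*Combined protocol and SAP*

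**What the plan says.** The study follows one cohort of app users with no concurrent control. The only comparison named is the hypothesis, under Statistical Considerations, that adolescents "will demonstrate similar results to the results previously found in adults".

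Under Efficacy Endpoints Analysis the whole model specification is: "Generalized linear mixed model (GLMM) will be used to compare the effect of treatment month on efficacy rate outcomes". Covariates, random effects, link function and unit of analysis are not stated.

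The outcome definitions, in the Efficacy endpoints row of the synopsis and again under Utilization Endpoints Analysis, treat baseline severity differently:

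- Freedom: "Pain/functional disability freedom will be calculated as a decrease from any pain/disability level at baseline to none at 2 h post-treatment". The synopsis spells this out as baseline scores of 1, 2 or 3 for both pain and disability.
- Pain relief: "Pain relief will be calculated as a decrease from severe or moderate levels at baseline to mild or none at 2 h posttreatment". Mild baselines do not enter.
- Disability relief: "Functional disability relief will be calculated as any improvement in disability from baseline to 2 h posttreatment".

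The Evaluable Treatment row requires baseline and 2-hour scores for both pain and disability, and the Data collection row lists them for extraction. The Baseline Data section names only age and gender. No outcome is planned by baseline severity, and no table of attack severity by month is described. Time from attack onset to treatment is not named in the extraction list, although the device description says "Nerivio is intended for self-administration at the onset of a migraine episode".

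**The concern.** On a 0 to 3 scale, a mild attack needs to fall one step to count as free and a severe attack needs three. It is plausible, though the documents do not quantify it, that freedom at 2 hours is more frequent from a mild baseline. A pooled freedom rate is then a weighted average whose weights are the shares of mild, moderate and severe attacks treated. If those shares differ between months, the rate differs between months.

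A model with month as its only effect cannot tell such a change in weights from a change in outcome at a given severity. A rise could be read as the treatment working better with continued use, and a fall as waning, when only the severity at which users start treatment has moved. A patient random intercept, if one is used, absorbs stable differences between users but not drift within a user.

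This point concerns the mix of baselines among valid treatments. It does not concern treatments with a zero baseline or users who stop reporting.

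**Working it through.** The documents state no rate, sample size, alpha or power, so there is no figure of the plan's own to reproduce. The check holds freedom constant within each baseline level, so that the true per-attack month effect is zero, and asks how far the pooled rate moves.

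**Inputs (all assumed).** The first-month mix is 20% mild, 50% moderate, 30% severe. In the later month the mild share is 20 points higher, taken from the other two in proportion: 40% mild, 37.5% moderate, 22.5% severe. Pain freedom from mild/moderate/severe is 50/25/12% (wide gradient), 40/25/15% (medium), 30/25/20% (narrow) or 25/25/25% (none).

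**Formula.** Pooled rate = sum over baseline levels of (share × rate).

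- Wide: 0.20×0.50 + 0.50×0.25 + 0.30×0.12 = 0.261; later 0.40×0.50 + 0.375×0.25 + 0.225×0.12 = 0.321.
- Medium: 0.20×0.40 + 0.50×0.25 + 0.30×0.15 = 0.250; later 0.40×0.40 + 0.375×0.25 + 0.225×0.15 = 0.288.
- Narrow: 0.20×0.30 + 0.50×0.25 + 0.30×0.20 = 0.245; later 0.40×0.30 + 0.375×0.25 + 0.225×0.20 = 0.259.

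| Gradient | First month | Later month | Spurious change | Odds ratio |
|---|---|---|---|---|
| Wide | 26.1% | 32.1% | +6.0 points | 1.34 |
| Medium | 25.0% | 28.8% | +3.8 points | 1.21 |
| Narrow | 24.5% | 25.9% | +1.4 points | 1.08 |
| None | 25.0% | 25.0% | 0 | 1.00 |

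The change is the shift in mild share times the gap between the mild rate and the average non-mild rate. In the wide case the non-mild average is (0.50×0.25 + 0.30×0.12)/0.80 = 0.201, and 0.20 × (0.50 − 0.201) = 0.060. The change is therefore proportional to the shift. Over shifts of 5 to 30 points it runs from 1.5 to 9.0 points (wide), 0.9 to 5.6 (medium) and 0.3 to 2.1 (narrow). A fall in the mild share reverses the sign.

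**Chance of a false finding.** This assumes 500 treatments in each of two months, independence and two-sided alpha 0.05. For the 20-point shift, the chance of a significant difference in the direction of the shift is about 55% (wide), 27% (medium) and 7% (narrow), against 2.5% with no shift.

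**Does adjustment remove it?** A small simulation used 150 patients over 12 months, with the mild share drifting from 20% to 40% and no true month effect. A logistic GEE with exchangeable correlation stood in for the GLMM. Adding baseline severity moved the odds ratio for month 12 against month 1 from 1.29 to 1.01 (wide), 1.15 to 0.98 (medium) and 1.05 to 0.98 (narrow). With 60 runs per scenario, the odds ratios are informative but the rejection rates are not.

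**The case against.** - **Silence is not exclusion.** The model sentence does not say that baseline severity is left out. This stands as a limit: the defect is a model that leaves the covariate open, which permits an unadjusted analysis or a choice made after seeing the data.
- **Two premises are not in the documents.** Neither a gradient in freedom by baseline level nor a drift in mix over months is stated. A reader might infer from the onset wording that users treat earlier as they gain experience. The documents do not support that: the sentence describes intended use and applies equally from the first month. This stands, so the point is conditional.
- **The figures are per treatment.** The plan's responder rule is per patient: the outcome in at least half of that patient's evaluable treatments. The effect on the responder rate may be larger or smaller and depends on treatments per user, which the documents do not give. This stands. It also means that the unit of the model must be fixed before the covariate has a meaning.
- **Adjustment can remove something real.** The device is described as for acute and/or preventive treatment. If repeated use made later attacks milder, baseline severity would partly be a result of earlier treatment. This stands, and it is why both the unadjusted and the adjusted result are needed.
- **Not every endpoint is equally exposed.** Pain relief excludes mild baselines, so only its moderate/severe mix can shift. Disability relief needs a one-point improvement from any level, so the one-step-against-three argument does not carry over.
- **The month model is supporting.** The stated hypothesis is similarity to adults, and no listed endpoint is a month trend. This is true, but it is the only efficacy model in the plan.

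**Conclusion.** The point holds in conditional form. The only efficacy model names treatment month and no baseline severity, the two freedom endpoints pool baselines 1 to 3, and the score that would separate them is recorded for every evaluable treatment. If freedom depends on baseline level and the baseline mix shifts between months, the month effect moves with no change in per-attack outcome. Under the assumed rates, a 20-point rise in the mild share gives about +1.4 to +6.0 points of pain freedom. Without a gradient or without a shift the effect is zero.

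A reader might go further and infer that the month result will be biased, or that the efficacy objective must be reworded because uncontrolled rates cannot be credited to the device. The documents support neither. They show no gradient and no drift. Stating an aim to evaluate efficacy in a study titled as real-world evidence does not attribute the whole rate to the device. The absence of a control is a separate limitation that no covariate repairs. Adjustment deals only with recorded severity.

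**What to change.** Under Efficacy Endpoints Analysis:

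- Fit the GLMM with the single evaluable treatment as the unit and a patient random intercept.
- Report the month effect both unadjusted and adjusted for the baseline score of the treated attack, using pain for the pain outcomes and disability for the disability outcomes.
- Report pain freedom and disability freedom separately for mild and for moderate/severe baselines, beside the pooled rate.
- Tabulate the mix of baseline scores by month, so that a reader can see whether any shift occurred.

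No change to the objective is needed.

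The cost is a little more analysis and two small tables, with no new data. The adjusted result answers a per-attack question only, because earlier device use could itself affect baseline severity. The text should say so where the two results are shown together.

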Utilization endpoints	

5. Consistent Usage of Migraine Abortive (Rescue) Medications: The proportion of subjects with REN treatments without the use of pharmacological migraine abortive (rescue) medication (either over the counter or prescribed), or with a combination of rescue medication or without any treatment at all at 2 hours post-treatment in at least 50% of all their treatments.

6. Treatment intensity distribution: The mean intensity of the stimulation collected for all treatments that were performed within the study

Safety endpoints	Rate of serious adverse events, adverse events and device-related adverse events

Data collection	
Data will be collected prospectively through the Nerivio smartphone application. At the time of creating a Nerivio account on the App, patients (and their parents, in case of patients younger than 18) are required to sign a consent statement presented to them, where they agree that their deidentified data may be collected and used for reserve purposes.
 
Prospective data was collected for Nerivio users in the United States who treated their migraine attacks with the Nerivio device. Nerivio utilization, and Nerivio treatment reports at T=0h and T=2h were extracted from the Nerivio server in an unidentified manner. Data will be analyzed per user following additional analysis per the target population.
 
The following data will be extracted:
 

• Demographics: Age at registration, gender.

• Treatment Details: Treatment date, baseline pain intensity, pain intensity at 2 hours post-treatment, baseline functional disability, functional disability at 2 hours post-treatment.

• Treatment Frequency: Number of treatments per month over the 12-months period.

• Pain Intensity: 0 (no pain), 1 (mild), 2 (moderate), 3 (severe).

• Functional Disability: 0 (no disability), 1 (mild interference), 2 (moderate interference), 3 (severe interference).

• Additional migraine symptoms (Nausea/ vomiting, Photophobia, Phonophobia)

Statistical considerations	See at the end of the document
Responder Definition	For each efficacy endpoint, a participants will be considered a responder if they achieved the defined outcome in at least 50% of their evaluable treatments during that study period.

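### The only efficacy model named concerns treatment month, while efficacy is defined as one whole-period responder status per user, and that responder proportion gets no stated estimate with an interval

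*Combined protocol and SAP*

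**What the plan says.** The document is a combined protocol synopsis and SAP.

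- **Model.** The whole of Efficacy Endpoints Analysis reads "Generalized linear mixed model (GLMM) will be used to compare the effect of treatment month on efficacy rate outcomes". It gives no unit of analysis, link function, random effects, definition of month or target quantity.
- **What efficacy means.** The Study Design row of the synopsis says "Treatment efficacy will be measured by consistent reduction in headache pain intensity and functional disability at 2-hours post-treatment". The Responder Definition row makes this a user-level status for each efficacy endpoint: the participant must have "achieved the defined outcome in at least 50% of their evaluable treatments during that study period".
- **Restated rule.** Under Utilization Endpoints Analysis the SAP adds "Consistent efficacy will be conducted in cases where at least two qualified treatments were performed", and defines responders as "Patients who experienced the outcome (e.g., pain freedom) in at least 50% of their reported treatments", limited to treatments without reported rescue medication.
- **Single-treatment wording.** The four efficacy endpoints are also worded for one treatment, for example "Reduction in functional disability by at least one point from baseline at 2 hours post-treatment". The Data collection row lists "Treatment date, baseline pain intensity, pain intensity at 2 hours post-treatment" among the items to be extracted.
- **Question posed.** The objective is to evaluate safety, utilization and efficacy in adolescents. The hypothesis, at the start of the statistical considerations, is that results resemble those previously found in adults. Neither mentions month.
- **Months elsewhere.** Apart from calendar dates, months appear only for treatment frequency, over a 12-month period.

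**The concern.** The section that should say how efficacy is estimated names a model for a different question. An analyst who follows it exactly obtains a comparison between months. The share of adolescents who respond consistently, which is the natural figure to set beside the adult results, is left without a stated estimator, denominator or interval.

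The sentence is also open on its outcome. Its efficacy rates could be per-treatment success or a responder status recalculated for each month. These are different quantities with different dependence on how often users treat, and the plan leaves the choice to be made after the data are seen.

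**Working it through.** The plan states no rate, sample size, alpha or power, so there is no figure to reproduce. The check is structural, with illustrations on assumed inputs.

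**1. Does the model match the responder endpoint?** The status covers all of a user's qualified treatments, so each user contributes one row per endpoint. Treatment month does not vary within that row, and a user random effect has no repeated values to work on. The month model cannot be fitted to that variable.

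**2. Does it match any outcome in the plan?** Yes. The single-treatment outcomes are binary, dated and repeated within user. A logistic mixed model with month as fixed effect and a user random intercept was fitted to simulated data (300 users, 1762 treatments over 12 months, true user SD 1 logit). It ran, with an estimated user SD of 0.94. The simulation shows feasibility only.

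**3. Do the candidate outcomes give the same number?** No. In the same simulated data:

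| Outcome | Rows | Rate |
|---|---|---|
| Success per treatment | 1762 | 58% |
| 50% rule within each user-month, no minimum | 1396 | 62% |
| 50% rule over the whole period | 300 | 68% |

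**4. How does the 50% rule depend on the number of treatments?** With n treatments and a common success probability p, the responder probability is P(X ≥ n/2), where X is Binomial(n, p). At p = 0.6 (assumed):

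- n = 2: 1 − 0.4² = 0.840
- n = 3: 3 × 0.6² × 0.4 + 0.6³ = 0.432 + 0.216 = 0.648
- n = 4: 1 − 0.4⁴ − 4 × 0.6 × 0.4³ = 1 − 0.0256 − 0.1536 = 0.821

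At p = 0.4 the same formula gives 0.640 at n = 2, 0.367 at n = 10 and 0.245 at n = 20. The per-treatment rate and the responder proportion are therefore different quantities.

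**5. Does this survive if users differ?** It shrinks but remains. All rows have a population success rate of 60%:

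| Between-user variation (assumed) | n = 2 | n = 3 | n = 4 | Spread |
|---|---|---|---|---|
| None | 84.0% | 64.8% | 82.1% | 19.2 points |
| Beta-binomial, ICC 0.1 | 81.6% | 63.5% | 78.0% | 18.1 points |
| Beta-binomial, ICC 0.5 | 72.0% | 60.8% | 67.5% | 11.2 points |
| Logit-normal, SD 2 logits | 74.6% | 61.5% | 69.8% | 13.1 points |

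The values alternate between even and odd n. A shift in treatment frequency would move monthly responder rates, but the direction depends on how the counts shift.

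**6. Which months?** January 2021 to May 2022 spans 12 + 5 = 17 calendar months, while the frequency item covers 12. The plan does not say whether treatment month is a calendar month or a month since first use.

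**The case against.** The strongest reply is that the endpoints are defined per treatment, dated records are extracted, and a mixed model of month is a standard analysis for such data. On this view the responder rule is a further summary, and the model was never meant for it. The Utilization section also says that consistent efficacy will be examined and gives the rule, which implies a descriptive proportion placed under the wrong heading. Counts and percentages are specified for categorical variables, although only under the demographic heading.

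Much of this stands, and it rules out three stronger readings that a reader might infer:

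- **That the month model cannot be fitted to the endpoints at all.** It can be fitted to the per-treatment outcomes. It cannot be fitted to the whole-period responder status. The reference to that study period is also loose enough that someone could redefine the status by month.
- **That the responder proportion goes unanalysed.** A descriptive proportion is implied. What is missing is an explicit estimator and an interval.
- **That the plan will produce a false month trend.** Nothing in the documents applies the 50% rule or the two-treatment minimum within months. The figures in steps 4 and 5 show what would happen on that route, using assumed rates.

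The reply does not remove the mismatch. Even on its best reading, the named model estimates how per-treatment success changes with month, which is neither the consistent efficacy the synopsis describes nor the question in the objective or hypothesis.

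**Conclusion.** The concern holds as a mismatch between the named model and the plan's own efficacy measure, together with an unspecified outcome for that model. Followed as written, the efficacy section does not estimate the responder proportion and does not bear on similarity to adults, and no section gives that proportion an interval. These conclusions rest on the text alone.

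The size can only be illustrated. If the 50% rule were applied within months, responder rates at 2, 3 and 4 treatments would differ by about 19 points when every user has 60% success, and by about 11 to 18 points under the user variation assumed above. The documents give neither success rates nor treatment counts, so these are not predictions. The correction should be made, and it is inexpensive.

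**What to change.** Replace the sentence in Efficacy Endpoints Analysis with two stated analyses.

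1. **Main.** For each of the four efficacy endpoints, report the proportion of responders among users with at least two qualified treatments, with a 95% confidence interval. Exact or Wilson are both acceptable; name one. Move the consistent-efficacy rule here from the Utilization section. The estimate and its interval can then be set against the adult results.
2. **Secondary.** Fit a logistic mixed model to success at 2 hours in each qualified treatment, with a participant random intercept and month as the fixed effect. Define month explicitly, for example as month since the user's first treatment, and reconcile the 12-month period with the 17-month window. Do not apply the 50% rule or the two-treatment minimum within months.

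The cost is SAP wording and slightly more analysis, on data already listed for extraction. The downside is that monthly results will be on the per-treatment scale and not directly comparable with the consistent-responder proportion; the report should say so.
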